3.3.4 Removal of patients from therapy or assessments

3.3.4.1 Removal of individual patients from therapy

The trial medication has to be permanently discontinued in the following circumstances

- The patient experiences signs of hepatic injury, defined in Section 5.3.7.1.
- In the opinion of the investigator, the patient experiences unacceptable adverse events despite dose adjustments and supportive care.
- Use of concomitant treatment: as defined in Section 4.2.2 "restrictions".
- Parenteral feeding requirement.
- Pregnancy (refer to Section 5.3.6).
- If a patient becomes pregnant during the trial the investigational product needs to be stopped and the patient should be followed up until birth or otherwise termination of the pregnancy. The data of the patient will be collected and reported in the clinical trial report (CTR) until patient's last visit and any events thereafter will be reported in the BI drug safety database. Refer to Section 5.3.6 for detailed information on event reporting in case of pregnancy.

In the following cases discontinuation of trial medication is highly recommended. Only in special circumstances, the Investigator, upon thorough assessment of all available clinical data and taking into consideration the potential risks associated with administration of nintedanib, may decide not to withdraw the trial medication, even though one or more of the below mentioned criteria are fulfilled. In such a case, continuation of treatment with trial

Page 34 of 126

Proprietary confidential information © 2018 Boehringer Ingelheim International GmbH or one or more of its affiliated companies

medication should be discussed with the patient, and the decision and reasoning documented in the source data.

- Major surgery, including any abdominal or intestinal surgery.
- Anti-coagulation. Patients who require full-dose therapeutic anticoagulation (e.g. vitamin K antagonists, heparin, hirudin, direct thrombin inhibitors, etc), or high-dose antiplatelet therapy. (Prophylactic low dose heparin or heparin flush as needed for maintenance of an indwelling intravenous device (e.g. enoxaparin 4000 I.U. s.c. per day), as well as prophylactic use of antiplatelet therapy (e.g. acetyl salicylic acid up to 325 mg/day, or clopidogrel at 75 mg/day, or equivalent doses of other antiplatelet therapy is allowed.).
- Major thrombo-embolic events e.g. stroke, deep vein thrombosis, pulmonary embolism, myocardial infarction.
- Increased risk of bleeding e.g. hemorrhagic CNS event, gross / frank haemoptysis or haematuria, active gastro-intestinal bleeding or GI-ulcers.

For conditions that allow treatment interruption please refer to Section 4.2.1.

Permanent discontinuation of trial medication (prematurely): if a patient permanently discontinues the trial medication prematurely, it is of utmost importance for the robustness and integrity of the trial results that his/her lung function parameters, other efficacy endpoints and safety data are further recorded until the end of the trial. Patients, who prematurely discontinue trial medication, will be asked to follow their original visit schedule (except the laboratory 'a-Visits'. refer to Section 6.2.2).

Vital status should be collected for all patients at week 52 and at week 100 or at the timepoint when with their last full visit would have been scheduled, whatever occurs earlier. Removal of individual patients from trial participation

An individual patient is to be withdrawn from trial participation if the patient withdraws consent for trial participation, without the need to justify the decision. Given the patient's agreement, the patient will undergo the procedures for trial discontinuation and follow up as outlined in the Flowchart and Section 6.2.3. For all patients, the reason for withdrawal (e.g. adverse events) must be recorded in the Electronic Case Report Form (eCRF). These data will be included in the trial database and will be reported.

3.3.4.2 Discontinuation of the trial by the sponsor

Boehringer Ingelheim reserves the right to discontinue the trial overall or at a particular trial site at any time for the following reasons:

• Failure to meet expected enrolment goals overall or at a particular trial site

Trial Protocol

Page 35 of 126

Proprietary confidential information © 2018 Boehringer Ingelheim International GmbH or one or more of its affiliated companies

- Emergence of any efficacy/safety information invalidating the earlier positive benefitrisk-assessment that could significantly affect the continuation of the trial
- Violation of Good Clinical Practice (GCP), the Clinical Trial Protocol (CTP), or the contract disturbing the appropriate conduct of the trial

c03014699-05 Trial Protocol Page 36 of 126

Proprietary confidential information © 2018 Boehringer Ingelheim International GmbH or one or more of its affiliated companies

4. TREATMENTS

4.1 TREATMENTS TO BE ADMINISTERED

4.1.1 Identity of BI investigational product(s)

Table 4.1.1: 1 Identity of BI investigational products

	Nintedanib	Placebo
Substance:	Nintedanib	-
Pharmaceutical formulation:	Soft gelatine capsule	Soft gelatine capsule
Source:	BI Pharma GmbH & Co. KG	BI Pharma GmbH & Co. KG
Unit strength:	150 mg, 100 mg	Placebo to 150 mg, 100 mg
Posology:	bid	bid
Route of administration:	Oral (swallowed)	Oral (swallowed)

4.1.2 Method of assigning patients to treatment groups

At Visit 1, patients who meet all entrance criteria will enter a screening period.

When a patient is qualified for entry into the randomised treatment period at Visit 2, treatment will be assigned via Interactive Response Technology (IRT). To facilitate the use of the IRT, the Investigator will receive all necessary instructions for using the IRT.

4.1.3 Selection of doses in the trial

Based on the efficacy, safety and dose-finding from trials investigating nintedanib in IPF, TOMORROW (P11-11216), INPULSIS I and INPULSIS II (P14-07514), a dose of 150 mg bid was selected. With 150 mg bid, acceptable tolerability in Systemic Sclerosis patients is expected based on the risk profile seen in IPF patients. Lower starting doses may not be expected to demonstrate efficacy based on the dose ranging trial (TOMORROW) in IPF. However, to manage adverse events, the dose may be reduced to 100 mg bid temporarily or permanently (refer to Section 4.2.1 and Section 6.2.4).

4.1.4 Drug assignment and administration of doses for each patient

The treatment for an individual patient will be assigned by means of an IRT contact during Visits 2, 4, 6, 7, 8, 9, 10, and 11. Patient will receive either active drug at a dosage of 150 mg bid or placebo bid.

Trial medication will consist of 1 capsule twice daily throughout the trial. Wallets covering 4 30 days + 5 days reserve treatment (1 wallet = 6 blisters with 10 capsules each, plus 1 blister reserve) will be dispensed to the patient:

• 1 wallet at day 1 (randomization = Visit 2) (30 days plus 5 days reserve).

- 2 wallets at Visit 4 (60 days plus 10 days reserve).
- 3 wallets at Visit 6 and Visit 7 (90 days plus 15 days reserve).
- 4 wallets at Visit 8 (120 days plus 20 days reserve).
- 4 wallets at Visit 9, 10 and 11 respectively (120 days plus 20 days reserve).

Trial medication will be administered orally on a twice daily basis (bid). The patients should swallow the trial medication unchewed together with a glass of water (~250 mL), and should observe a dose interval of 12 hours. Trial medication needs to be taken at the same time every day (between 06:00 and 11:00 in the morning, and between 18:00 and 23:00 in the evening). Because nintedanib may cause stomach discomfort, it is recommended to take the trial medication with food intake.

A forgotten dose should be skipped if the time window to the next dose is less than 8 hours. The next dose should be taken as scheduled.

The investigational product should only be dispensed to participating patients according to the protocol by authorised personnel as documented in the form "Investigator's Trial Staff".

In case of adverse events requiring dose reduction between planned visits, an additional site visit is required. 100 mg bid (or matching placebo) will be assigned by means of an IRT call from the Investigator (refer to Section 6.2.4). The color of capsules (100 mg capsule or corresponding placebo) will be slightly different but the packaging will remain the same (same number of capsules per blister and same number of blisters per wallet).

The dose can be reduced without prior interruption, i.e., immediately stepping down from 150 mg bid to 100 mg bid if necessary due to adverse events which requires a special trial visit according to procedures described in Section 4.2.1.

If the reduced dose is well tolerated, re-escalation is possible within 4 weeks (after the dose reduction visit), which if it occurs between scheduled trial visits will also require a special trial visit according to procedures described in Section 4.2.1.

Patients experiencing adverse events requiring temporary interruption of trial medication may re-start trial medication according to procedures described in Section 4.2.1.

4.1.5 Blinding and procedures for unblinding

4.1.5.1 Blinding

This trial is a double-blind trial.

Trial medication is identified by a medication code number. Packaging and labelling will be otherwise identical. The booklet cover page for 150 mg and 100 mg nintedanib and the respective corresponding placebo is differently coloured. Colour, size and shape of

nintedanib and placebo capsules are indistinguishable within dose strength, but are different between dose strengths.

Patients, investigators and everyone involved in trial conduct or analysis or with any other interest in this double-blind trial (apart from the DMC) will remain blinded with regard to the randomised treatment assignments until after database lock.

The randomization code will be kept secret by the sponsor's clinical trial support up to database lock.

The DMC may review unblinded data upon request, and only under conditions that ensure that patients, investigators and everyone involved in trial conduct or analysis or with any other interest in this double-blind trial will remain blinded.

4.1.5.2 Unblinding and breaking the code

Emergency unblinding will be available to the Investigator store manager via IRT. It must only be used in an emergency situation when the identity of the trial medication must be known to the Investigator in order to provide appropriate medical treatment or otherwise assure safety of trial participants. The reason for unblinding must be documented in the source documents along with the date and the initials of the person who broke the code and information needs to be entered on the appropriate eCRF page.

For Japan:

In this blinded trial, an emergency code break will be available to the Investigator / the sub-Investigators via the IRT system. This code break may only be accessed in emergency situations when the identity of the trial medication must be known to the Investigator / the sub-Investigators in order to provide appropriate medical treatment or if required to assure the safety of trial participants. Each site receives a manual from the IRT provider that contains instructions on how to unblind the treatment of a patient via the IRT (via 24-hour emergency helpline). If the code break for a patient is accessed, the Sponsor must be informed immediately. The reason for accessing the code break, together with the date, must be documented on the appropriate eCRF page. In case third party needs to break the code, however, when the Investigator cannot be reached, the code can be opened by calling emergency code manager.

4.1.6 Packaging, labelling, and re-supply

Primary trial material will be capsules containing 150 mg of nintedanib (or 100 mg of nintedanib if dose is reduced), and matching placebo. All trial medication will be packaged in blister cards. Each blister card will contain 10 capsules. Seven blisters cards will be packaged into one child-resistant tamper-evident wallet (i.e. 70 capsules/wallet). Each wallet will be labelled with a multi-language booklet according to the requirements of the participating countries.

Proprietary confidential information © 2018 Boehringer Ingelheim International GmbH or one or more of its affiliated companies

One wallet covers for one month of treatment.

Details of packaging and the description of the label will be provided in the ISF.

Initial supply and further re-supplies will be managed by an IRT. The IRT will assign an appropriate kit to each patient according to the randomization list that are generated by the Sponsor and not known by the trial personnel.

Re-supplies of trial medication are planned due to the short expiry date and the long duration of the trial. The medication for re-supply will be packaged in an identical manner as the medication for initial supply.

4.1.7 Storage conditions

Drug supplies will be kept in their original packaging and in a secure limited access storage area according to the recommended storage conditions on the medication label. A temperature log must be maintained for documentation.

If the storage conditions are found to be outside the specified range, the local clinical monitor (as provided in the list of contacts) must be contacted immediately.

All unused trial medication must be returned to the Sponsor or appointed CRO. Receipt, usage and return must be documented on the respective forms. Account must be given for any discrepancies.

4.1.8 Drug accountability

The Investigator will receive the investigational drugs delivered by a clinical research organisation (CRO) appointed by the Sponsor, when the following requirements are fulfilled:

- Approval of the trial protocol by the institutional review board (IRB) / ethics committee (EC).
- Availability of a signed and dated clinical trial contract between the Sponsor and the head of the investigational site.
- Approval/notification of the regulatory authority, e.g. competent authority.
- Availability of the curriculum vitae of the Principal Investigator.
- Availability of a signed and dated clinical trial protocol.
- In countries where it is required, availability of the proof of a medical license for the Principal Investigator.
- In the US, availability of Form 1572.

The Investigator must maintain records of the product's delivery to the trial site, the inventory at the site, the use by each patient, and the return to the Sponsor or appointed CRO.

Trial Protocol

Page 40 of 126

Proprietary confidential information © 2018 Boehringer Ingelheim International GmbH or one or more of its affiliated companies

These records will include dates, quantities, batch / serial numbers, expiry ('use-by') dates, and the unique code numbers assigned to the investigational product and trial patients. The Investigator will maintain records that document adequately that the patients were provided the doses specified in Section 4.1.4 and reconcile all investigational products received from the Sponsor. At the time of return to the Sponsor or appointed CRO, the Investigator must verify that all unused or partially used drug supplies have been returned by the clinical trial patient and that no remaining supplies are in the Investigator's possession.

4.2 CONCOMITANT THERAPY, RESTRICTIONS, AND RESCUE TREATMENT

4.2.1 Rescue medication, emergency procedures, and additional treatment(s)

Rescue medications to reverse the action of nintedanib are not available.

Dose reduction (from 150 mg bid to 100 mg bid) or treatment interruption should be considered to manage adverse events. No further dose reduction is possible for patients on the 100 mg bid regimen. In case of persistent adverse events observed at this dose, or severe effects at 150 mg bid, permanent treatment discontinuation should be considered.

Treatment interruption and reduction and reescalation are repeatedly possible.

Table 4.2.1: 1 Allowed treatment reduction / interruption periods:

	AEs considered drug related	AEs not considered drug related
Maximum interruption	4 weeks	8 weeks
Recommended restart	with reduced dose (100 mg bid)	with the same dose (100 mg bid or 150 mg bid)
Re-escalation	within 4 weeks to 150 mg bid	

4.2.1.1 Management of diarrhoea

Other causes for diarrhoea should always be considered and treated accordingly (e.g. viral infections, SSc related diarrhoea, bacterial overgrowth, antibiotic treatment).

Diarrhoea should be managed as early as possible after onset of first symptoms with standard antidiarrhoeal symptomatic treatment, e.g. loperamide.

If diarrhoea persists despite optimal symptomatic treatment, treatment interruption and dose reduction of nintedanib should be considered based on the recommendations described in Table 4.2.1.1: 1.

Table 4.2.1.1: 1 Management of diarrhoea (considered related to trial medication)

Description	Symptomatic Treatment*	Action with trial medication
Diarrhoea with increase of <4 stools per day over baseline ¹ .	Initiate anti-diarrhoeal medicines at first signs of symptoms (e.g. 4 mg loperamide followed by 2 mg after each loose stool or every 2-4 hours to a maximum of 16 mg/day) until bowel movements cease for 12 hours.	Continue same trial medication dose.
Diarrhoea with increase of 4 to 6 stools per day over baseline ¹ .	Initiate/continue anti-diarrhoeal medicines; If diarrhoea of this severity persists for ≥48 to 72 hours assess for dehydration and electrolyte imbalance; In addition, consider IV fluids and electrolyte replacement as clinically indicated.	If diarrhoea persists for ≥48 to 72 hours despite optimal symptomatic care: 1. Interrupt trial medication until recovery. 2. Reduce dose to 100 mg bid after recovery. 3. Re-escalate to 150 mg bid within 4 weeks if deemed clinically appropriate.
Diarrhoea with increase of ≥7 stools per day over baseline¹; stool incontinence, or life threatening consequences.	Follow recommendations above. In addition, consider stool workup to exclude infectious colitis; adequate IV fluid replacement ≥24 hours, hospitalisation as clinically indicated; consider referral to a GI specialist to rule out potential differential diagnoses.	 Interrupt trial medication until recovery. Reduce dose to 100 mg bid after recovery. Consider re-escalation within 4 weeks to 150 mg bid if deemed clinically appropriate. In case of reoccurrence of diarrhoea of this severity despite optimal symptomatic treatment and dose reduction, treatment with trial medication should be permanently discontinued.

Footnotes:

^{*} Other causes for diarrhoea should always be considered and treated accordingly (e.g. viral infections, SSc related diarrhoea, bacterial overgrowth, antibiotic treatment)

¹ Baseline defined as usual stools/day prior randomisation.

4.2.1.2 Management of liver enzyme elevation

Evaluate the concomitant use of other drugs known to cause liver enzyme elevations. For a detailed guidance on how to manage liver enzyme elevations, please refer to Table 4.2.1.2: 1.

Table 4.2.1.2: 1: Recommendations for managing liver enzyme elevations

	AST or ALT increase to			Signs of hepatic injury*
	>1.5x to <3x ULN	≥3x to <5x ULN and no signs of hepatic injury (Section 5.3.6)	≥5x to <8x ULN and no signs of hepatic injury (Section 5.3.6)	(Section 5.3.6)
Visit 2 (randomization)	Withdraw trial medication or justify continuation ¹	Withdraw trial medication	Withdraw trial medication	Withdraw trial medication
Any other Visit	Continue as planned ²	Reduce dose or interrupt trial medication ³	Interrupt trial medication	Withdraw trial medication CLINICAL
		Close observation ⁴	Close observation ⁴	EVALUATION OF HEPATIC-INJURY (Section 5.3.6)
		After 2 weeks or any time later	After 2 weeks or any time later	
	<3x ULN	≥3x ULN	<3x ULN	>3x ULN
	Reduced: return to initial dose.	Permanently discontinue trial medication	Restart at reduced dose	Permanently discontinue trial medication.
	Interrupted: restart at reduced dose. Monitor bi- weekly for at least 8 weeks	Close observation ⁴	Monitor weekly for 4 weeks, then bi-weekly for at least 8 weeks	Close observation ⁴

Footnotes:

*Signs of hepatic injury are defined as

- ALT and/or AST ≥8 fold ULN
- ALT and/or AST ≥3 fold ULN and total bilirubin ≥2 fold ULN
- ALT and/or AST ≥3 fold ULN and unexplained INR >1,5
- ALT and/or AST ≥3 fold ULN and unexplained eosinophilia (>5%)
- ALT and/or AST ≥3 fold ULN and appearance of fatigue, nausea, vomiting, right upper abdominal quadrant pain or tenderness, fever and/or rash

phosphatase, total bilirubin, and eosinophils within 48 to 72 hours, then approximately 7 days, then approximately 2 weeks by using intermediate visit lab kit.

¹ Investigator to confirm in writing that continuation is justified (e.g. intermittent fluctuation of transaminases).

² According to visit schedule. Consider additional control visits as adequate.

³ To be decided by Investigator, based on individual risk assessment.

⁴Close observation: Re-test ALT and AST, alkaline

Page 43 of 126

Proprietary confidential information © 2018 Boehringer Ingelheim International GmbH or one or more of its affiliated companies

Initial assessment of liver enzyme elevation should be performed at the investigational site. Blood samples for additional monitoring may be collected at the investigational site, primary care physician or external laboratory with specific trial lab kits and sent to the central laboratory for analysis.

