The term AESI relates to any specific AE that has been identified at the project level as being of particular concern for prospective safety monitoring and safety assessment within this trial, e.g. the potential for AEs based on knowledge from other compounds in the same class. AESI need to be reported to the Sponsor's Pharmacovigilance Department within the same timeframe that applies to SAE, see Section 5.3.7.

Adverse events relating to gastrointestinal perforation and hepatic injury will be considered AESIs.

Hepatic injury

In this trial protocol, signs of hepatic injury are defined as:

- ALT and/or AST ≥8 fold ULN
- ALT and/or AST \geq 3 fold ULN and total bilirubin \geq 2 fold ULN*
- ALT and/or AST \geq 3 fold ULN and unexplained INR > 1,5*
- ALT and/or AST \geq 3 fold ULN and unexplained eosinophilia (>5%)*
- ALT and/or AST ≥3 fold ULN and appearance of fatigue, nausea, vomiting, right upper abdominal quadrant pain or tenderness, fever and/or rash

These lab findings constitute a hepatic injury alert and the patients showing these lab abnormalities need to immediately stop the trial medication and need to be followed up according to the "DILI checklist" provided in the ISF.

^{*} in the same blood draw sample.

c03014699-05 Page 59 of 126

Proprietary confidential information © 2018 Boehringer Ingelheim International GmbH or one or more of its affiliated companies

In case of clinical symptoms of hepatic injury (icterus, unexplained encephalopathy, unexplained coagulopathy, right upper quadrant abdominal pain, etc.) without lab results (ALT, AST and total bilirubin) available, the investigator should make sure these parameters are analysed, if necessary in an unscheduled blood test. Should the results meet the criteria of hepatic injury alert, the procedures described in the DILI checklist should be followed.

Intensity of AEs

The intensity of the AE should be judged based on the following:

Mild: Awareness of sign(s) or symptom(s) that is/are easily tolerated

Moderate: Enough discomfort to cause interference with usual activity

Incapacitating or causing inability to work or to perform usual activities Severe:

In addition the intensity of diarrhoea adverse events should be classified and recorded in the eCRF according to the Common Terminology Criteria for adverse events (CTCAE) version 4 (R10-4848, Table 5.3.7:1).

Table 5.3.7:1 CTCAE Categorisation for diarrhoea

CTCAE Grade	Diarrhoea
1	Increase of <4 stools per day over baseline

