5.4.4 Liver enzyme and bilirubin elevations

Liver enzyme and bilirubin elevations will be reported using the three following definitions:

- (ALT and/or AST ≥ 3 fold ULN) AND bilirubin ≥ 2 fold ULN^[1]
 - And ALKP ≥ 2 xULN
 - And ALKP < 2 xULN
- ALT ≥ 5 fold ULN and/or AST ≥ 5 fold ULN
- ALT ≥ 3 fold ULN and/or AST ≥ 3 fold ULN

^[1] These elevations are defined within a time window of 30 days i.e. the elevation of bilirubin should appear within 30 days after the elevation of AST and/or ALT.

The proportion of patients presenting signs of hepatic injury will be summarised, based on the following definition for signs of hepatic injury:

- ALT and/or AST ≥ 8 fold ULN
- ALT and/or AST ≥ 3 fold ULN and total bilirubin ≥ 2 fold ULN in the same sample
- ALT and/or AST ≥ 3 fold ULN and unexplained INR > 1.5 in the same sample
- ALT and/or AST ≥ 3 fold ULN and unexplained eosinophilia ($>5\%$) in the same sample
- ALT and/or AST ≥ 3 fold ULN and appearance of fatigue, nausea, vomiting, right upper abdominal quadrant pain or tenderness, fever and/or rash within ± 7 days of the abnormal ALT and/or AST laboratory test result (please refer to [Section 9.6](#) for the list of relevant MedDRA preferred terms to support the derivation of a potential hepatic injury)

In addition, maximum individual elevations based on worst value on treatment will be defined as:

- ≥ 3 fold ULN; ≥ 5 fold ULN; ≥ 8 fold ULN for AST and ALT
- ≥ 1.5 fold ULN; ≥ 2 fold ULN for bilirubin
- ≥ 1.5 fold ULN; ≥ 2 fold ULN for ALKP
- ≥ 1 fold ULN; ≥ 3 fold ULN for GGT

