C4	Trial medication not interrupted when ALT or AST \geq 5 fold ULN	Based on liver enzyme elevation and interruptions reported between baseline and Week 52 Automatic IPV	None
C5	Trial medication not permanently discontinued after signs of liver enzyme elevations were observed that a) are indicative of hepatic injury as defined in Section 5.3.7.1 of the CTP b) correspond to ALT or AST \geq 3 fold ULN despite dose reduction or treatment interruption for 2 weeks or more	All patients where signs of liver enzyme elevations (between baseline and Week 52) are not dealt with according to the requirements of the CTP. Manual IPV based on review of MQRM listings	None
C6	Medication code broken inappropriately	Reason for medication code broken is inappropriate (e.g. not emergency) and data collected after unblinding between baseline and Week 52 Review of MQRM listings and / or to be identified at the site level on the manual PV log / issue log.	None
D	Concomitant Medication		
D1	Patient received prohibited concomitant therapies between baseline and Week 52 (see Section 4.2.2.1 of the CTP)	Based on concomitant therapies reported between baseline and Week 52 Review of MQRM listings and / or to be identified at the site level on the manual PV log / issue log	None

Table 6.2: 1 Important protocol violations over 52 weeks (cont'd)

Category/Code	Description	Requirements	Excluded from
E	Missing data		
E1	Patient without any physical assessment for more than 6 months, although under study medication	Missing results for physical assessment for more than 6 months during the trial Automatic IPV	None
E2	No baseline or post-baseline FVC assessments up to Week 52	Automatic IPV	None
E3	No baseline or post-baseline mRSS up to Week 52	Automatic IPV	None
E4	No reliable ^[1] baseline or post-baseline SGRQ total score up to Week 52 ^[1] As per exclusion criteria 24	No baseline or post-baseline value or exclusion criteria 24 met Automatic IPV	None

Automatic PVs are those detected via an automated programming process using SAS.

Note: IPV's E2, E3 and E4 will be not be reported over the whole trial period.

A summary of IPV decisions will be provided in the final BRPM minutes.

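### The liver management table and Protocol 5.3.7.1 classify hepatic injury differently when the findings fall in separate blood draws

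*Protocol*

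**What the plan says.** **Protocol 4.2.1.2.** Table 4.2.1.2:1 sets the action by ALT/AST level and by whether there are signs of hepatic injury. Its footnote defines those signs in five items, among them "ALT and/or AST ≥3 fold ULN and total bilirubin ≥2 fold ULN" and "ALT and/or AST ≥3 fold ULN and unexplained INR >1,5". No item carries a condition on when the two findings must occur. A patient with any of the signs is to be withdrawn from trial medication. For the definition the table refers to Section 5.3.6.

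**Protocol 5.3.7.1.** The same five items appear with the same thresholds. The bilirubin, INR and eosinophil items carry an asterisk, explained as "in the same blood draw sample". Patients who meet the definition "need to immediately stop the trial medication and need to be followed up" using the DILI checklist. Hepatic injury is also an AESI, reported on the SAE timeline.

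**Protocol 3.3.4.1.** The list of mandatory permanent discontinuations includes "The patient experiences signs of hepatic injury, defined in Section 5.3.7.1".

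**SAP.** Section 5.4.4 uses the one-sample form, for example "ALT and/or AST ≥ 3 fold ULN and total bilirubin ≥ 2 fold ULN in the same sample". Important protocol violation C5(a) covers elevations that "are indicative of hepatic injury as defined in Section 5.3.7.1 of the CTP". Section 7.8.1.1 identifies hepatic-injury AESIs from what the investigator reports on the eCRF.

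**The concern.** The protocol defines a permanent-stop rule twice, and the two definitions differ for three of the five criteria. The table is where a site looks when it handles a raised liver result. Its own reference leads to a section on worsening or new SSc organ involvement, so the table does not lead the site to the other definition.

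Two things are at stake for patients whose ALT/AST rise and second finding come from different draws. One is whether trial medication is stopped permanently. The other is whether the investigator reports a hepatic AESI. Both could depend on the page the site used. The AESI tabulation would inherit that variation, because it rests on investigator reporting.

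**Working it through.** No sample size, power or event figure is involved, so the check is a comparison of two rules.

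**1. The rules for the three affected criteria.** Call bilirubin ≥2x ULN, unexplained INR >1.5, or unexplained eosinophils >5% a second finding.
- Section 5.3.7.1: some single draw has ALT/AST ≥3x ULN and a second finding.
- Table footnote, read literally: some draw has ALT/AST ≥3x ULN, and some draw, not necessarily the same one, has a second finding.

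Any patient who meets the first rule meets the second. The reverse fails when the findings are split. The other two criteria (ALT/AST ≥8x ULN, and ALT/AST ≥3x ULN with symptoms) are the same in both places.

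**2. Constructed cases.** The laboratory values are assumptions chosen to show the logic. INR and eosinophil findings are taken as unexplained, and no symptoms are assumed. Multiples are of ULN.

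| Draws | 5.3.7.1 | Footnote, literal |
|---|---|---|
| ALT 3.5x with bilirubin 2.2x, one draw | Yes | Yes |
| ALT 8.5x alone | Yes | Yes |
| ALT 3.5x, bilirubin 1.5x; then ALT 3.2x, bilirubin 2.2x | Yes | Yes |
| ALT 4x, bilirubin 1.5x; then ALT 2.8x, bilirubin 2.2x | No | Yes |
| ALT 6x, bilirubin 1.5x; then ALT 2.9x, bilirubin 2.2x | No | Yes |
| a-Visit ALT 3.5x (no INR in panel); then ALT 2.8x, INR 1.6 | No | Yes |
| a-Visit ALT 3.5x (no eosinophils in panel); then ALT 2.8x, eosinophils 6% | No | Yes |

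The rules disagree only where ALT/AST has fallen below 3x by the draw that shows the second finding, or where the second finding was not measured in the draw with the elevation.

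**3. What follows in the table for a split-draw patient.** If the patient counts as hepatic injury, trial medication is withdrawn. If not, ALT 4x falls in the ≥3x to <5x column (reduce or interrupt) and ALT 6x in the ≥5x to <8x column (interrupt), both with close observation. If ALT/AST is below 3x at two weeks or later, the first column lets a reduced patient return to the initial dose and an interrupted patient restart at the reduced dose. The second column restarts at the reduced dose. The contrast is therefore permanent withdrawal against reduction or interruption.

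**4. Can split findings arise?** Close observation calls for re-tests at 48 to 72 hours, about 7 days and about 2 weeks. The a-Visit panel in Protocol 5.3.3 lists neither INR nor eosinophils, and the close-observation re-test list omits INR. Split findings are therefore possible. Nothing in the documents says how often they would occur.

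**5. Effect on the SAP outputs.** The hepatic-injury proportion in 5.4.4 and violation C5(a) each use one fixed same-sample definition. C5(a) would not flag a split-draw patient kept on drug contrary to the table, and a patient withdrawn under the table need not count in 5.4.4.

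**The case against.** The strongest reply is that a governing definition exists. The mandatory-stop rule in 3.3.4.1 names 5.3.7.1, Protocol 5.3.3 sends readers to 3.3.4 for withdrawal criteria, and the table is titled as recommendations. The footnote is silent on timing and does not state an opposing rule. This stands in part, and it narrows the ambiguity. It does not remove it: the footnote is a complete definition in its own right, its only reference is wrong, and the protocol states no order of precedence.

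Four stronger readings are tempting, and the documents do not support them.
- *The same patient stops at one site and simply continues at another.* Different handling is possible, not certain, and the other branch is dose reduction or interruption.
- *Split findings are the expected pattern.* Regular visits measure ALT, AST, bilirubin, INR and the differential count together, and close observation re-tests ALT, AST, bilirubin and eosinophils together. The four discordant cases of seven above were constructed and are not a frequency.
- *Violation counts and the SAP hepatic-injury proportion depend on the page a site read.* C5(a) and 5.4.4 apply the 5.3.7.1 definition whatever the site did, and C4 and C5(b) rest on ALT/AST thresholds.
- *The footnote leaves on drug someone whom 5.3.7.1 requires to stop.* Read literally, the footnote is the broader rule, so it cannot. The fatal liver injury mentioned in Protocol 2.3 therefore adds no weight in that direction.

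**Conclusion.** The inconsistency is real and limited. The footnote to Table 4.2.1.2:1 and Section 5.3.7.1 give different classifications for patients whose ALT/AST elevation and bilirubin, INR or eosinophil finding fall in different draws, and the table's reference to 5.3.6 is wrong. For those patients the action may be permanent withdrawal or reduction/interruption, and stops and investigator-reported hepatic AESIs could differ between sites. The number of patients cannot be derived from the documents. SAP 5.4.4 and C5(a) are consistent with 5.3.7.1 and are not themselves in error.

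This rests on a literal reading of the footnote, with no implied same-draw condition. The footnotes are out of order in the extracted text, but all five criteria are legible and no same-draw wording appears among them. The point deserves correction because it concerns a permanent-stop and AESI definition and the repair is small.

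**What to change.** Reconcile the footnote to Table 4.2.1.2:1 with Section 5.3.7.1 so that one definition applies, stating whether the paired findings must come from one draw. Correct the table's references from 5.3.6 to 5.3.7.1. Inform the sites of the reconciled definition. The sponsor's clinical team decides which version stands.

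If the 5.3.7.1 definition is kept, the SAP needs no change. If it changes, update SAP 5.4.4 to match; C5(a) follows automatically because it cites 5.3.7.1. The cost is one footnote, one corrected cross-reference and a site letter.
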